3000 IU of heparin and 50 mcg of Nitrocine will be administered in each renal artery. The Interventional Radiologist will gain percutaneous femoral access to introduce the 7Fr Terumo destination sheath under aseptic technique. 0.36-mmdiameter guide wire will be introduced via the arterial puncture. This will be followed by insertion of a 6Fr Symplicity SpyralTM (Medtronic) catheter. Once electrodes are well apposed angiographically and impedance values and tracings are stable, radiofrequency (RF) energy will be delivered to the treatment site. The four electrodes simultaneously deliver RF energy for 60 seconds. Final renal angiogram will be obtained to check the integrity of the renal artery. Closure device will be used for all patients to allow early ambulation.

Sham Procedure

In the control group, the sham procedure will consist of only a renal angiogram. Participants will undergo diagnostic renal angiogram but will not receive any therapeutic endovascular treatment. The diagnostic catheter will be kept *in situ* and dummy radiograph scan will be performed for another 10–15min before removing the femoral sheath from the sedated patient. Participants will remain on the procedure table for at least 20 min after the angiogram to prevent possible unblinding of randomisation allocation.

Risk associated with the procedure

The primary risks of the procedure are similar to the risks of all diagnostic procedures requiring catheterization of the arteries. The following are possible risks of the catheterization procedure, which includes the renal angiogram (with or without the denervation procedure):

Uncommon < 10%, temporary and not severe unless otherwise indicated

- Nausea or vomiting
- Complications associated with the use of any pain or anxiety medication during or after the procedure
- Complications at catheter insertion site in the groin
- > Pain
- Bruising
- ➤ Hematoma (collection of blood outside a blood vessel)

Rare < 1%, temporary and not severe unless otherwise indicated

- Heart rhythm disturbances, including bradycardia (a slowed heart rate)
- Embolism Formation and dislodgement of a blood clot or dislodgement of cholesterol/plaque
 within the blood vessel, which travels downstream into small vessels, blocking blood flow and
 causing temporary or permanent damage to organs in the body. Clots are known to cause heart

attack, stroke, kidney damage, or threaten circulation to arms or legs and may ultimately lead to incapacitation or death.

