- Complications at catheter insertion site in the groin
- > Pseudoaneurysm (injury to the artery wall resulting in a build-up of blood under the skin)
- AV fistula (an abnormal connection or passageway between an artery and a vein)
- Vascular complications requiring surgery
- Perforation or dissection of a blood vessel, such as the renal artery (unintended puncture through the wall of a blood vessel, such as a renal artery, requiring repair)
- Hypotension (blood pressure too low)
- Hypertension (blood pressure too high)
- Complications associated with the contrast agent used during the procedure, e.g., serious allergic reaction or reduced kidney function.
- Complications associated with medications commonly utilized during the procedure known risks
 of medications commonly used during the procedure (e.g., narcotics, anxiolytics, other pain
 medications, anti-vasospasm agents).

Very Rare < 0.1%

- Complications at catheter insertion site in the groin
- ➤ Infection (localized redness, heat swelling and pain at the catheter insertion site)
- ➤ Significant bleeding (blood loss from the catheter insertion site requiring surgery or transfusion of 2 or more units of packed red blood cells (PRBCs).
- Retroperitoneal bleeding (bleeding into the retroperitoneal space). Vascular complications requiring surgery damage to an artery (e.g., femoral) or vein requiring surgical repair.
- Cardiopulmonary arrest
- Death

There are additional risks that could possibly be associated with the denervation procedure/response to treatment. These complications have not yet been quantified.

These potential risks may include:

- Pain: during or after the procedure that may require treatment with pain medications.
- Damage to one or both kidneys and/or loss of kidney function: perforation of kidney or an occlusion of blood flow to the kidney (e.g., from stenosis or embolism) and/or reduction of glomerular filtration rate. If severe enough, this could require dialysis.

- Renal artery aneurysm: localized weakening and ballooning of the renal artery from the interventional procedure or the delivery of RF energy.
- Renal artery stenosis: narrowing of the renal artery due to the interventional procedure or the delivery of RF energy.
- Arterial spasm or constriction: Acute or chronic narrowing of the renal artery lumen diameter at denervation locations due to arterial muscle contraction, local tissue contraction or local edema.

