The study may involve unknown or unforeseen side effects or complications other than those mentioned above. If the above complications occur, they may lead to repeat or prolonged hospitalization, repeat procedures, emergency surgery, other emergency procedures, or, in rare cases, death. Although there are risks associated with participation, there will be a panel of physicians independent of the study, will monitor the safety of the study. They will be overseeing the safety of all study participants.

Risk Evaluation:

In this study we will use Symplicity SpyralTM denervation system. The safety, efficacy and performance of renal denervation treatment using Symplicity SpyralTM denervation system has been tested in pre-clinical and clinical studies. The safety and performance of the SymplicityTM multi-electrode radiofrequency renal denervation system was assessed in a prospective, non-randomised, open label, feasibility study. This study confirms the safety of treating patients with uncontrolled hypertension with the Symplicity multi-electrode radiofrequency renal denervation system. Minimal safety complications were reported, none of which was directly related to the delivery of radiofrequency energy (Table 1). In a recent SPYRAL HTN-OFF MED trial using Symplicity SpyralTM catheter, no major procedural or clinical safety events were observed in either the renal

denervation or sham control groups throughout the 3 months. Specifically, there were no deaths or occurrences of myocardial infarction, stroke, major bleeding, serum creatinine elevation greater than 50%, significant embolic events, vascular complications, renal artery re-intervention, new or worsening renal failure, or hypertensive emergency or crisis.

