Overall safety analysis of renal denervation system has been very positive. Renal denervation trials using first and second generation symplicity catheter from Medtronic have reported no serious procedure-related or device-related complications and occurrence of adverse events. Renal denervation procedure performed using catheters from other companies including St Jude Medical and Boston scientific have reported no serious or life threatening adverse events. Vascular complications seem rare and are not usually irreversible. So far, minor vasospasm of the renal artery post-denervation, small hematomas, pseudo-aneurysms, minor bleeds, and one dissection requiring stenting have been reported. Endothelial injury at the site of ablation lesions seems to be transient and reendothelization occurs soon enough. Clot formation at ablation sites can be prevented by appropriate antithrombotic and antiplatelet therapy. Renal artery stenosis seems to be a concern, but indeed, only two cases of renal artery stenosis due to renal nerve ablation have been reported so far, while the procedure has been already performed in several thousand patients. No major renal deterioration has been reported so far. In addition we did not identify any complications in our single centre study in 60 patients who underwent the procedure (for hypertension and LPHS) over the last 4 years.

The risk associated with the procedure also depends on the experience of interventionalist carrying out the intervention. In this study renal denervation procedure will be performed by an experienced and trained interventional radiologist who has performed RDN in close to 60 patients (for loin pain and hypertension). His clinical experience with the procedure and the skill that he has gained will be helpful in minimizing the potential risks. In addition we will take following steps to minimize the risk.

Minimization of Risk

The following measures will also be taken to minimize risk to participants as part of this investigational plan:

- 1. Physicians and staff will receive appropriate training prior to using the system. Training will include instruction on equipment and lab setup, assessing renal anatomy, intra-procedural patient management and monitoring, Symplicity Catheter delivery and RF ablation, and post-procedural care.

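### Does the safety table's 3/50 rate of vascular complications contradict the under-1% band the protocol gives for pseudoaneurysm?

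*Protocol*

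**What the plan says.** Risk associated with the procedure opens by saying that "The primary risks of the procedure are similar to the risks of all diagnostic procedures requiring catheterization of the arteries". It then lists risks in uncited frequency bands, stated to cover the angiogram whether or not denervation is added. Groin haematoma falls in the under-10% band. Groin pseudoaneurysm falls under "Rare < 1%, temporary and not severe unless otherwise indicated", with no other severity given. A separate list follows of risks tied to denervation itself, described as not yet quantified.

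Risk Evaluation says that trials with the first and second generation catheters "have reported no serious procedure-related or device-related complications", and that "Vascular complications seem rare and are not usually irreversible". The same paragraph names pseudoaneurysms and small haematomas among reported events. It adds that the site saw no complications in 60 patients treated for hypertension or loin pain. A cited sham-controlled trial of the Spyral catheter is reported as free of vascular complications; its size is not given.

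The safety table, taken from a non-randomised study in uncontrolled hypertension, has a vascular complications row of 3 (6.0%) at n=50. Its footnote says all three patients had pseudoaneurysm, two of them with haematoma as well, and gives a major adverse event rate of 6%.

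**The concern.** The protocol chose this table as its safety evidence, and the table's one non-zero vascular row is six times the ceiling of the band assigned to that event. The row carries the same label, vascular complications, that Risk Evaluation calls rare. Events that make up a 6% major adverse event rate also sit awkwardly beside a summary that reports nothing serious.

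The bands apply to both arms, and sham participants are due a second catheterization when they cross over after six months. If the access risk were understated, an ethics board would be weighing too favourable a figure, and one event among ten participants could look surprising when it should not. The section also shows signs of loose editing: vascular complications requiring surgery appear under both the under-1% and the under-0.1% headings.

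**Working it through.** **Inputs.** From the safety table: 3 events in 50. From Risk Evaluation: 0 in 60. From the risk list: a ceiling of 1%. From Study Population: 10 participants.

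**1. The plan's own figure.** 3/50 = 0.060, as printed. The exact (Clopper-Pearson) 95% interval is 1.25% to 16.5%.

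**2. The table against the band.** With X binomial (n = 50, p = 0.01):
- P(X = 0) = 0.99^50 = 0.605
- P(X = 1) = 50 × 0.01 × 0.99^49 = 0.306
- P(X = 2) = 1225 × 0.01² × 0.99^48 = 0.076
- P(X ≥ 3) = 0.014 (from unrounded terms)

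Taken alone, the table fits 1% poorly.

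**3. The site's series against each rate.** 0/60 has an exact 95% interval of 0% to 6.0%.
- At a true 1%: P(0 of 60) = 0.99^60 = 0.55
- At a true 6%: P(0 of 60) = 0.94^60 = 0.024

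The site's data cannot establish a rate below 1%, but they fit 6% about as badly as the table fits 1%.

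**4. Do the two series differ?** Given three events in 110 patients, the chance that all three fall among the 50 is C(50,3)/C(110,3) = 19,600/215,820 = 0.091. The opposite extreme, all three among the 60, is more probable (34,220/215,820 = 0.159), so the two-sided Fisher P is 0.091. They do not clearly differ.

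**5. Pooled.** 3/110 = 2.7%, exact 95% interval 0.6% to 7.8%. P(X ≥ 3 | n = 110, p = 0.01) = 0.099. The point estimate is above 1%, but the interval includes rates below it. The cited Spyral trial cannot be added without its size; with no vascular complications it could only lower the pooled estimate.

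**6. What this trial could show.** The chance of at least one event in n procedures is 1 − (1 − p)^n.
- n = 10: 9.6% at 1%, 46% at 6%
- n = 15 (assuming five sham participants cross over): 14% at 1%, 60% at 6%

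Even if the band were right, a single event would not be remarkable, so one event in a trial this small would not settle which rate is right.

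**7. Where the bands are used.** Participant's Safety/Discontinuation sets out the safety committee's make-up, its meetings, the data sent at 6 weeks, 3 and 6 months, and the decision to discontinue or modify consent. It gives no expected rate or threshold and does not mention the bands. Statistics reports no sample size calculation and limits the analysis to thematic and non-parametric methods. Nothing in either section takes the bands as an input.

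**The case for a change.** The best case for a change is that the band has no source and the protocol's only tabulated evidence points above it. An access-site reading of the three events is reasonable: the table lists them as post-procedural, apart from its renal rows; two also had haematoma, which the protocol lists as a groin complication; and Risk Evaluation says no complication was directly related to radiofrequency delivery. Haematoma at 2/50 = 4.0% fits its own under-10% band, so the mismatch is specific to pseudoaneurysm. A wording repair would cost almost nothing.

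Much of this stands. The band is unsupported by the protocol's own evidence, and a reader has to notice the discrepancy unaided. Three things limit it.

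- **Not like for like.** A general catheterization figure is set against one denervation study that states neither the site of the events nor the closure method. This protocol uses a closure device for every patient, so whether 6% carries over is unknown.
- **Loose words, not figures.** Calling vascular complications rare summarises experience across manufacturers in several thousand patients and is not tied to 1%. The table's major events are nowhere equated with the serious complications of the summary.
- **No demonstrated use.** It is tempting to say the safety committee would judge events against the bands, but the protocol does not say so. The nearest link is the feasibility question about the probability of unexpected adverse events. It does not define unexpected by these bands, and pseudoaneurysm is a listed risk whichever band it sits in.

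The double listing looks clerical. The second entry, "Vascular complications requiring surgery damage to an artery (e.g., femoral) or vein requiring surgical repair", is run on after retroperitoneal bleeding in a list whose nesting is already mixed.

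**Conclusion.** The observation is accurate, but no change to the plan follows. An uncited band below 1% stands beside a printed 3/50 (6.0%, 1.25% to 16.5%). With the site's 0/60 the protocol's countable evidence is 3/110 (2.7%, 0.6% to 7.8%), which does not settle whether the true rate is below 1%. The pooling assumes that the two series are comparable and that the site's report of no complications includes pseudoaneurysm; the table's events are only inferred to be at the access site.

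The less favourable figure is disclosed in full, footnote included, so an ethics reviewer or committee member can weigh it. Re-banding the event or adding a cross-reference would alter descriptive text only: no design feature, analysis, threshold or monitoring decision would differ. The consent pages are not in this copy, so nothing is concluded about what participants are told. The point is editorial.

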- 2. The system's design and software include several safety mechanisms to reduce risk to the patient (limitations on temperature, time, impedance, and power delivered to the patient).

- 3. Patients will be closely monitored during the procedure and at regularly scheduled intervals for the duration of the study.
- 4. Physicians will employ usual and customary clinical technique (e.g., sterile technique during catheter use and aseptic wound care procedures).
- 5. Appropriate sedatives and narcotics will be used during the procedure to minimize discomfort associated with the shock.
- 6. During follow-up sessions, any side effects will be identified and treated accordingly.

Table 3. Safety events at 6 and 12 months.

Safety measures, n (%)		6 months (n=50)	12 months (n=49)
Death*		0 (0%)	0 (0%)
Cardiovascular events	Myocardial infarction	1 (2%)	1 (2%)
	Hypertensive crisis/emergency*	0 (0%)	0 (0%)
	Stroke	0 (0%)	0 (0%)
	Hospitalisation for new onset heart failure	0 (0%)	0 (0%)
	Hospitalisation for atrial fibrillation	0 (0%)	0 (0%)
Renal events	Renal artery reintervention due to perforation or dissection*	0 (0%)	0 (0%)
	New onset end-stage renal disease*	0 (0%)	0 (0%)
	Serum creatinine elevation >50%	(2) 4%	(2) 4.1%
	Significant embolic event resulting in end-organ damage*	0 (0%)	0 (0%)
	New renal artery stenosis >70%*	0 (0%)	0 (0%)
Post-procedural events	Vascular complications*	3 (6.0%)¶	

Numbers are defined as mean±standard deviation or no. (%). *The major adverse event rate is 6% (3/50 events) and defined as the one-month rate of all safety events and the six-month rate of new renal artery stenosis >70% as shown with asterisks. *Three patients with pseudoaneurysm, two of whom also had haematoma.

Table 1: Safety evaluation of Symplicity[™] multi-electrode radiofrequency renal denervation system (20)

Measures

Following measures will be taken at baseline, 6 weeks and 3 and 6 month after the procedure:

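### Does the Risk Evaluation's statement that no major renal deterioration has been reported conflict with the protocol's own safety table in a way that needs a change?

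*Protocol*

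**What the plan says.** Under Risk Evaluation, the protocol reviews earlier experience with renal denervation. It says that trials of the manufacturer's first and second generation catheters "have reported no serious procedure-related or device-related complications and occurrence of adverse events", and later that "No major renal deterioration has been reported so far". Of one hypertension trial it says that "no major procedural or clinical safety events were observed", and it spells this out with a list that includes "serum creatinine elevation greater than 50%, significant embolic events, vascular complications".

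Table 1, placed after Minimization of Risk, gives counts from a single-arm study of the multi-electrode system in 50 hypertensive patients. Its renal rows include "Serum creatinine elevation >50" per cent, with 2 of 50 at 6 months and 2 of 49 at 12 months. Its footnote states "The major adverse event rate is 6% (3/50 events") and describes the vascular events as "Three patients with pseudoaneurysm, two of whom also had haematoma".

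Under Risk associated with the procedure, the protocol names loss of kidney function and renal artery stenosis among the possible denervation risks and adds "These complications have not yet been quantified".

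Participant's Follow-up Regimen fixes the questionnaires at baseline, 6 weeks, 3 months and 6 months. The next sentence adds demographics, blood count, electrolytes, creatinine, urine analysis and eGFR without repeating the times. The Measures section lets the follow-up assessments be made by telephone or face to face.

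**The concern.** A creatinine rise above 50% is listed as an example of a major event when the protocol reports that one trial had none. The same event, present in 2 of 50 patients in the protocol's only table of safety counts, then goes unmentioned in a sentence that denies major renal deterioration. The denial of serious procedure-related complications likewise sits beside a 6% major adverse event rate, and the remark that denervation risks are unquantified sits beside a table with counts for two of them.

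If the prose were the working background, the safety committee could start from too favourable a view of kidney harm. All 10 participants are due to receive denervation, the sham group after 6 months. A creatinine rise cannot be detected in a telephone call, so if no blood sample were tied to the follow-up times, the feasibility question on how well adverse events are identified could not be answered for this event.

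**Working it through.** **The table's figures.** 2/50 = 4.0% and 2/49 = 4.1%, as printed; 3/50 = 6.0%, as printed. The protocol gives no intervals. The exact (Clopper-Pearson) 95% limits are beta quantiles: lower = B(0.025; x, n − x + 1), upper = B(0.975; x + 1, n − x).

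| Event | x/n | Rate | Exact 95% interval |
|---|---|---|---|
| Creatinine rise >50%, 6 months | 2/50 | 4.0% | 0.5% to 13.7% |
| Creatinine rise >50%, 12 months | 2/49 | 4.1% | 0.5% to 14.0% |
| Major adverse event | 3/50 | 6.0% | 1.3% to 16.5% |

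**What 4.0% would mean for 10 denervations.** Expected events: 10 × 0.04 = 0.4. Chance of at least one: 1 − 0.96^10 = 0.335, or 34%. At the interval limits it is 1 − (1 − 0.0049)^10 = 4.8% and 1 − (1 − 0.1371)^10 = 77%. This shows how little 50 uncontrolled patients with another disease can say; it is not a forecast. The centre's own 60 patients without complications should not be pooled with the 2/50, because the protocol does not say that creatinine was measured in all of them.

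**Is the renal sentence contradicted?**

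- The protocol does not define major renal deterioration.
- The table's major-event composite counts only asterisked rows. As the text was read, the creatinine row has no asterisk. New end-stage renal disease does, and was 0/50 and 0/49.
- The list for the hypertension trial names the creatinine rise and new or worsening failure of the kidney as separate items, so the protocol does not equate them. It does place both under the word major.
- Risk Evaluation states, citing Table 1, that none of the few complications in that study arose directly from applying radiofrequency energy.

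The sentence conflicts with the table on one reading of an undefined term and agrees with it on another.

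**Is the complications sentence contradicted?** The same paragraph goes on to report pseudo-aneurysms, small haematomas and a dissection that needed a stent, so these kinds of event are disclosed. What is left is a tension between denying serious complications and the table's 6% labelled major.

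**Is the remark on quantification wrong?** It concerns risks that may come from denervation itself. Counts from 50 patients without a control group do not measure risk attributable to denervation, so the remark can stand.

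**Is kidney function left unmonitored?** The laboratory sentence follows directly on the one that fixes the four times and is worded as an addition to it. The risk section refers to blood tests that the study requires. Participant's Safety/Discontinuation sends data to an independent researcher at 6 weeks, 3 months and 6 months. The telephone option closes a section on questionnaires, a diary and a diagnostic interview, and does not say that blood is not drawn. Study Timeline refers to a scheme in appendices that are not shown.

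**The case for a change.** The strongest case for a change is consistency. The protocol's own prose treats a creatinine rise above 50% as a major safety event when it is absent, and never mentions it when it is present. The renal sentence speaks of what has been reported, not of what was caused, so the statement on radiofrequency causation does not fully answer it. Kidney function loss is a named risk, everyone is to be denervated, and the safety committee's concerns can lead to discontinuation or a revised consent form. Correcting the prose would cost only text, and tying blood samples to the follow-up times would cost little: at most 10 × 3 + 5 × 3 = 45 samples, if the arms are equal, all sham participants cross over and the three times are repeated.

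Part of this stands. The two Risk Evaluation sentences are kinder than the table, and the laboratory sentence would be clearer with its times stated. But the risk is not hidden. The counts are printed in full shortly after the prose, and the risk section warns of kidney damage, reduced filtration and possible dialysis. A safety committee that reads the protocol sees both.

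**Conclusion.** No change to the plan is called for. The counts and intervals are right, and the wording is loose: the prose gives a better picture than the 2/50 creatinine rises and the 3/50 major adverse events support. But no number, decision rule, endpoint or analysis in this trial is derived from those sentences. The protocol makes no sample size calculation and derives no safety limit from these rates. Rewording the background would leave the design, conduct and analysis as they are.

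The sampling times are a gap that the team can fill sensibly: creatinine and eGFR are to be collected, and the four times stand in the sentence before. A clarifying phrase, and an alignment of the two sentences with the table, would be reasonable housekeeping at the next revision.

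This conclusion assumes that the laboratory sentence is meant to follow the stated follow-up times, or that the timeline appendix says so, and that a telephone questionnaire does not replace the blood sample. If the appendix showed baseline bloods only, the monitoring part would need another look. The table's asterisks are also taken as they were read from the PDF.
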